10.5.3 Full analysis set: Secondary Effectiveness Analysis

The full analysis set for the secondary analysis (FAS_secondary), will consist of the main and supplementary cohort subjects who meet the criteria described in the preceding section for FAS_primary.

10.5.4 Per protocol

The per protocol (PP) analysis set will consist of all subjects with valid Primary Patency measurements at 6 months and with no major protocol violations.

Handling of missing data: Only observed data will be used in the PP analysis set.

10.5.5 Functionality dialysis sets

The functionality endpoints are relevant only for patients with specific dialysis status as applicable per the endpoint. Therefore, the following subsets of patients will be defined to analyze dialysis functionality endpoints.

Ongoing Dialysis Subset

Document title: VasQ FDA pivotal Protocol	Document No. CD0121	Revision 12.0 14 March 2021	Page 37 of 42
--	------------------------	-----------------------------------	------------------

This subset will include patients already on hemodialysis at study entry (index procedure).

Any Dialysis Subset

This subset will include patients who are either already on dialysis at study entry or started hemodialysis during the study. For patients who started the dialysis during the study, the start date will be determined as the earliest date reported among all dialysis sections.

This subset will be used to analyze “Fistula use for dialysis” and “Duration between Fistula First Use for Dialysis and final abandonment” endpoints.

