4 STUDY DESIGN

4.1 Structure

This is a prospective, multi-center, single-arm, open label study enrolling patients in the US, who are referred for creation of a new AV fistula. The VasQ will be applied to the AV fistula in all patients. The primary effectiveness endpoint for this trial will be measured at 6 months and compared to a performance goal (PG). Patients will be followed up for an additional 18 months for a total of 2 years. Additionally, this trial has several secondary endpoints. 129 patients will be enrolled with upper arm fistulas + 15 patients with forearm fistulas.

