6.4 Endpoint definitions

1. Primary patency: The time of access creation or placement until any first intervention (endovascular or surgical) to maintain or restore blood flow, or first occurrence to access thrombosis.

[REDACTED]

[REDACTED]

[REDACTED]

[REDACTED]

[REDACTED]

[REDACTED]

[REDACTED]

[REDACTED]

[REDACTED]

Proportion of patients (rate) with primary patency can be calculated at defined time points.

2. Secondary patency: the time of access creation or placement until access abandonment, and includes all surgical and endovascular interventions.
Proportion of patients (rate) with secondary patency can be calculated at defined time points.
3. Primary failure: Fistula permanent failure before hemodialysis suitability.
Proportion of patients (rate) with primary failure can be calculated at defined time points.
4. Primary assisted patency: The time of access creation or placement until any first intervention (endovascular or surgical) to restore blood flow of a thrombosed access, first occurrence to access thrombosis.
5. Maturation: Vein diameter $\geq 5\text{mm}$ and blood outflow ≥ 500 (-50) mL/min by Doppler ultrasound or fistula is used for dialysis.
Proportion of patients (rate) with mature fistulas can be calculated at defined time points.

Document title: VasQ FDA pivotal Protocol	Document No. CD0121	Revision 12.0 14 March 2021	Page 16 of 42
--	------------------------	-----------------------------------	------------------

6. Time to fistula maturation (physiological): the time (in days) between the fistula placement to date of the earliest confirmation of Vein diameter $\geq 5\text{mm}$ and flow volume in either artery or vein (at least one of them) ≥ 500 (-50) mL/min
7. Time to 100% Functional Fistula Dependency (applicable to patients who enter the study on dialysis): The time (in days) between the fistula placement to the start date of the first 4-week period in which the fistula was the only access available for administration of dialysis.
8. Fistula used for hemodialysis: Proportion of patients (rate) dialyzed through the study fistula. The rate can be calculated at defined time points.
9. Duration between fistula first use for dialysis and final abandonment: The time interval (in days) between first study fistula use for dialysis and the last confirmed use. [REDACTED]
10. Steal³ – Moderate or severe limb ischemia when graded as follows:

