17. Target artery /target vein diameter at 1, 3 and 6 months by Doppler measurement - *FAS primary and FAS secondary analysis sets*.
18. Target artery / target vein PSV (Peak Systolic Velocity, cm/sec) - *FAS primary and FAS secondary analysis sets*
19. Proportion of fistulas used for hemodialysis at 3 and 6 months post AVF creation - *Any dialysis subset*.
20. Duration between fistula first use for dialysis and final abandonment – *any dialysis subset*

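### The denominator for exploratory endpoint 19 (fistula use at 3 and 6 months) includes patients who first start hemodialysis after the time point

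*Combined protocol and SAP*

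**What the plan says.** Section 10.5.5 of the combined protocol and SAP gives the reason for having dialysis subsets: "The functionality endpoints are relevant only for patients with specific dialysis status as applicable per the endpoint". The Any Dialysis Subset is then defined as follows: "This subset will include patients who are either already on dialysis at study entry or started hemodialysis during the study". Where dialysis begins after entry, "the start date will be determined as the earliest date reported among all dialysis sections". The use of the subset is stated directly: "This subset will be used to analyze “Fistula use for dialysis” and “Duration between Fistula First Use for Dialysis and final abandonment” endpoints".

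Section 10.6.6, item 19, names the same subset for "Proportion of fistulas used for hemodialysis at 3 and 6 months post AVF creation". Item 20, duration of use, has it too. The endpoint definition in section 6.4, item 8, reads "Fistula used for hemodialysis: Proportion of patients (rate) dialyzed through the study fistula. The rate can be calculated at defined time points". It does not require that a patient be on dialysis by the time point.

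The study period is given in section 4.1: "Patients will be followed up for an additional 18 months for a total of 2 years". Sections 7.5 to 7.10 collect dialysis status, with start and stop dates, at months 1, 3, 6, 9, 12 and 24. Section 10.6.6 makes all secondary endpoints exploratory and descriptive, with 95% confidence intervals.

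**The concern.** Membership of the subset depends on what happens at any time up to month 24, but the endpoint is read at months 3 and 6. A patient who first needs hemodialysis at month 14 could not have been dialysed through the fistula at month 3 or 6. Under the stated rule that patient is in both denominators as a non-user. This has two consequences.

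- The proportion mixes how well the fistula serves dialysis with when patients came to need dialysis. That does not fit the reason section 10.5.5 gives for the subsets, since a patient not yet on dialysis lacks the relevant status at that time point.
- Membership can grow after the time point has passed. The 3- and 6-month figures can then change with no new 3- or 6-month data. Section 11.6 foresees publication once the 6-month data are analysed, so an early figure and a final figure for the same endpoint could disagree.

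At stake is the interpretation of one descriptive secondary endpoint and its confidence interval.

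**Working it through.** **Plan's own figure.** There is none to reproduce. The documents give no expected value for endpoint 19, no share of patients on dialysis at entry and no distribution of start times.

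**Inputs from the documents.** The subset has no cut-off at 3 or 6 months (10.5.5). It is assigned to endpoint 19 (10.5.5; 10.6.6, item 19). Follow-up is 24 months (4.1).

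**Algebra.** At time point t, let x be the patients dialysed through the study fistula, D the subset patients who started hemodialysis by t, and L those who start after t. Late starters cannot be in x.

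- Proportion as planned: x/(D+L)
- Proportion among those started by t: x/D
- Relative shortfall: 1 − [x/(D+L)]/[x/D] = 1 − D/(D+L) = L/(D+L)

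The shortfall is therefore the share of the subset that starts late. It is zero if L = 0. If that share is assumed to be 5% to 25%, the relative shortfall is 5% to 25%. With use of 70% among those started (assumed), this is 0.70 × 0.05 = 3.5 points to 0.70 × 0.25 = 17.5 points.

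**Month 3 against month 6.** D+L is the same total at both time points. Everyone who is late for month 6 is also late for month 3, so the relative shortfall at month 3 is at least as large as at month 6.

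**Illustration at month 6 (all counts assumed).** Of 144 enrolled, 86 are on dialysis at entry, 100 have started by month 6 and 70 use the fistula at month 6. Then x/D = 70/100 = 70.0%, whatever happens later. As planned:

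| Late starters L | x/(D+L) | Difference (points) | L/(D+L) |
|---|---|---|---|
| 0 | 70/100 = 70.0% | 0 | 0% |
| 7 | 70/107 = 65.4% | 4.6 | 6.5% |
| 14 | 70/114 = 61.4% | 8.6 | 12.3% |
| 29 | 70/129 = 54.3% | 15.7 | 22.5% |

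The month-6 observations are identical in every row. Only later events differ.

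**Wider range (also assumed).** The inputs were 129 or 144 enrolled, 50% to 70% on dialysis at entry with another 10% started by month 6, use of 50% to 90%, and late starters equal to 5% to 20% of enrolment. The shortfall then runs from about 3 to 23 points.

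**Started by t is not the same as on hemodialysis at t.** Let A be the patients actually on hemodialysis at the assessment. Those who started and then stopped, died, received a transplant or were lost before t are in D but not in A, so A ≤ D and x/A ≥ x/D. The formula above measures only the effect of late starters. A denominator of A also removes these patients, by a number the documents do not give.

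**The case against.** The strongest reply is that this is a missing sentence and not a planned error. An analysis set can be a pool that need not serve as the denominator at every visit. Section 10.5.5 derives a dialysis start date for patients who start during the study. Endpoint 20 does not need it, because section 6.4, item 9, measures from first to last use of the fistula. The only other endpoint given this subset is endpoint 19, so the date may have been meant to decide who counts at each time point. This reading is plausible, but no section states it. A programmer following 10.5.5 and 10.6.6 literally would use the whole subset.

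A second reply is that late starters may be few. Section 5.3 describes patients with end-stage disease who need access for dialysis. It expects those not yet covered by Medicare to become eligible within several months. This stands as a reason not to assume a large effect. It does not exclude one: the subset definition itself provides for patients who start after entry.

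A third reply is that analysing only data up to month 6 would cure the problem. It would cure month 6, but patients starting between months 3 and 6 would stay in the month-3 denominator. The final analysis could still change both figures.

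It is also fair that the error can only lower the apparent use of the fistula, so it cannot produce a falsely favourable result. Endpoint 19 is not the only measure of dialysis function either. Endpoints 5 (first successful cannulation) and 9 (full fistula dependency) use the Ongoing Dialysis Subset, which is fixed at entry and does not have this problem.

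**Conclusion.** The point holds as a defect in a stated rule for one exploratory endpoint. Taken literally, the plan counts patients not yet on hemodialysis as non-users at months 3 and 6. The relative shortfall is L/(D+L). The algebra needs no outside data, but its size here cannot be known from the documents, and every numerical example above rests on assumed counts.

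A reader might infer more than the documents support:

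- *That the reported proportion will certainly be too low.* It will be only if at least one patient starts after the time point and at least one is using the fistula then.
- *That a particular gap, such as 15 points, is to be expected.* No dialysis counts are given; only a range under stated assumptions is defensible.
- *That two conflicting reports of endpoint 19 are planned.* Section 11.6 allows publication after the 6-month data, but no section schedules this endpoint for reporting twice.
- *That the trial's main conclusion is affected.* The primary test uses FAS_primary (10.6.3) and the sample size rests on primary patency (10.4). Neither uses this subset, so the test, alpha and sample size stand.

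**What to change.** For endpoint 19, state in sections 10.5.5 and 10.6.6 that the denominator at each time point is the subjects on hemodialysis at that assessment. This means a hemodialysis start date on or before it, and no stop of hemodialysis, death, transplant or loss to follow-up before it. Say that stopping means stopping hemodialysis altogether, so that a patient dialysed through another access stays in the denominator as a non-user. Report the number excluded for each reason at each time point. Keep the Any Dialysis Subset as defined for endpoint 20.

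The cost is a few sentences. Start and stop dates and the access used are already collected at each follow-up visit. The small downside is a smaller denominator and a somewhat wider interval. In the illustration with 14 late starters, and assuming all 100 who had started are still on hemodialysis, the approximate 95% half-width goes from 1.96 × √(0.614 × 0.386/114) = 8.9 points to 1.96 × √(0.70 × 0.30/100) = 9.0 points.

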10.6 Statistical analysis

10.6.1 Overview

The data will be summarized in tables listing the mean, standard deviation, median, minimum, maximum and number of subjects for continuous data, or in tables listing count and percentage for categorical data where appropriate. Data listing by subject will be provided.

All statistical analyses will be performed and data appendixes will be created using the SAS® system, Version 9.2 or higher. The effects of noncompliance, dropouts, and possible covariates such as age, gender, and center, will be assessed to determine the impact on the general applicability of results from this study.

Safety and subject disposition analyses will be done on the safety analysis set. Primary effectiveness analyses will be done on FAS_primary and PP. Secondary [REDACTED] will be tested on FAS_secondary and PP. Primary and secondary [REDACTED] endpoints will be assessed hierarchically, so that the latter will be tested only if the former’s null was rejected.

10.6.2 Subject disposition

Subject disposition will be tabulated; the number of enrolled, exposed, prematurely terminated and completed subjects will be summarized, including the number of subjects in each analysis set. A list of dropouts will be prepared including reason for discontinuation, and time of discontinuation.

10.6.3 Primary effectiveness analysis

The primary effectiveness endpoint, Primary Patency at 6 months post procedure, will be tested in the FAS_primary using the following hypotheses:

- $H_0: (\text{Primary Patency Rate})_{\text{observed}} \leq 55.0\%$
- $H_1: (\text{Primary Patency Rate})_{\text{observed}} > 55.0\%$

Hypotheses will be tested using a two-sided, 95% Exact Binomial confidence interval about the observed 6-month Primary Patency rate. We will declare success on this endpoint if the lower limit of the confidence interval is above 55.0%. Note that if there will be missing values and MI will be applied, we will apply Exact Binomial computations to each of the multiple data sets, then use SAS® PROC MIANALYZE to obtain a P-value for the combined results.

10.6.4 [REDACTED] Secondary Analysis

The [REDACTED] secondary effectiveness endpoint, Primary Patency at 6 months post procedure, will be tested in the FAS_secondary using the following hypotheses:

Document title: VasQ FDA pivotal Protocol	Document No. CD0121	Revision 12.0 14 March 2021	Page 38 of 42
--	------------------------	-----------------------------------	------------------

- H_0 : (Primary Patency Rate)_{observed} \leq 55.0%
- H_1 : (Primary Patency Rate)_{observed} $>$ 55.0%

Testing will be done only if the null of the primary hypothesis in the preceding section will have been rejected (i.e. hierarchical testing). The statistical method used for testing will be identical to that of the primary hypothesis.

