10.4 Sample size justification

Presentation of sample size in this trial is based on the observed Primary Patency rate meeting a PG of 55% (see Section 10.1). Based on limited historical information on the use of VasQ our conservative estimate of device performance is a Primary Patency rate of 70%. A sample of N = 116 evaluable subjects will provide 90% power to demonstrate VasQ meeting the PG. To account for an approximate 10% dropout rate, 129 subjects will participate in this trial. Power computations are based on Exact Binomial computations with a two-sided Alpha = 0.05, designed to demonstrate that the lower

Document title: VasQ FDA pivotal Protocol	Document No. CD0121	Revision 12.0 14 March 2021	Page 36 of 42
--	------------------------	-----------------------------------	------------------

bound of the 95% Exact Binomial confidence interval about observed Primary Patency is above the 55% PG.

In summary, $N = 129$ subjects will be included in this trial to provide 90% power to demonstrate that the VasQ meets its PG.

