10.5.2 Full analysis set: Primary Effectiveness Analysis

The full analysis set for the primary effectiveness analysis (FAS_primary) will, consistent with ICH Guideline E9, include all subjects (with brachiocephalic fistulas) for whom the study device was implanted and for whom there is at least one post-procedure Primary Patency measurement.

Handling of missing data: Patients occluded prior to 6 months will be scored as failures even if missing subsequent observations. Patients with missing primary patency at 6 months, but with observed primary patency at later visits (without undergoing interventions) will be considered Success.

Because MI assumes missing at random (MAR), we will conduct sensitivity analyses to assess the sensitivity of our results to alternative assumptions of missingness (see below).

Subjects who died or underwent transplant before 6 months, and were non-occluded at that time of the event, will be excluded from the FAS and reported separately. If such subjects were occluded at or before the time of the event (death or transplant), they will be considered failures and included in FAS for the purpose of the primary analysis.

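### If any 6-month patency value is multiply imputed, the pooling step in 10.6.3 does not work as written and does not yield the stated success criterion

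*Combined protocol and SAP*

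**What the plan says.** Section 10.6.3 sets the test: "Hypotheses will be tested using a two-sided, 95% Exact Binomial confidence interval about the observed 6-month Primary Patency rate". The decision rule follows: "We will declare success on this endpoint if the lower limit of the confidence interval is above 55.0" percent. The next sentence covers imputation. It opens "Note that if there will be missing values and MI will be applied" and then gives this instruction: "we will apply Exact Binomial computations to each of the multiple data sets, then use SAS® PROC MIANALYZE to obtain a P-value".

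Multiple imputation (MI) appears in one other place, section 10.5.2, and only through its assumption: "Because MI assumes missing at random (MAR), we will conduct sensitivity analyses to assess the sensitivity of our results to alternative assumptions of missingness". The paragraph before that gives deterministic rules. Earlier occlusion counts as failure, and patency seen later without intervention counts as success.

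Section 10.6.4 applies the same statistical method to the hierarchical secondary test on the combined cohorts. Section 10.4 sets the error level: "Power computations are based on Exact Binomial computations with a two-sided Alpha = 0.05".

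**The concern.** There are two separate gaps.

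First, the input. Rubin's rules, which MIANALYZE applies, need a point estimate and a standard error from each imputed data set. Clopper-Pearson limits and exact P-values come from binomial tail probabilities and supply no such pair. The programmer must substitute something, such as the proportion with its Wald standard error or a transformed proportion, and the plan does not say what. Whatever is substituted, the result is no longer the exact test.

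Second, the output. Success is defined on a lower confidence limit. The MI step returns a P-value with no null value, no sidedness, no threshold and no pooled limit. MIANALYZE tests against zero unless told otherwise, and a test of patency against zero would always succeed.

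At stake is the decision rule for the two tests in the hierarchy whenever imputation is used.

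**Working it through.** **Inputs.** Performance goal 55.0% (10.6.3); expected rate 70%, two-sided alpha 0.05, 116 evaluable, about 10% dropout, 129 enrolled, 90% power (10.4). The plan gives no imputation model. I assume values missing completely at random and imputation from a Beta posterior.

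**The plan's own figures.** The smallest count out of 116 whose exact lower limit exceeds 55% is 75 (64.7%, lower limit 55.24%). P(X ≥ 75 | 0.55) = 0.0222 and P(X ≥ 75 | 0.70) = 0.911. Also 116/0.90 = 128.9, so 129. Sample size and power reproduce.

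**What pooling requires.** With estimates q_i and variances u_i from M data sets, the pooled estimate is the mean of the q_i. Its variance is T = W + (1 + 1/M)B, where W is the mean of the u_i and B is the variance of the q_i. The test is (pooled estimate − null)/√T. An exact analysis supplies no u_i.

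**A case where the readings disagree.** Take 74 successes in 116 observed, 13 missing, N = 129, M large, and a Beta(74.5, 42.5) posterior. Pool the raw proportion with its Wald variance.
- Pooled rate: (74 + 13 × 74.5/117)/129 = 82.278/129 = 0.6378.
- B: 13 × 0.6368 × 0.3632 × (1 + 12/118)/129² = 3.313/16641 = 0.000199.
- W: (0.6378 × 0.3622 − 0.0002)/129 = 0.001789.
- T = 0.001988, so the standard error is 0.0446.
- Lower limit: 0.6378 − 1.96 × 0.0446 = 0.5504. Test statistic: 0.0878/0.0446 = 1.97, two-sided P = 0.049. This passes.
- The exact lower limit on the 116 observed is 54.35%, which fails. About 46% of the imputed data sets pass the exact rule.

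With 73 successes, the same calculation gives P = 0.077 two-sided but 0.039 one-sided. The unstated sidedness alone can therefore change the result.

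**Error rates.** Simulated at a true rate of 55% with N = 129, M = 50 and 40,000 runs (Monte Carlo standard error about 0.08 points at these rates):

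| Missing | Raw pooling, two-sided P < 0.05, favourable direction | Raw pooling, one-sided P < 0.05 | Exact rule, observed cases |
|---|---|---|---|
| 4 | 2.7% | 5.8% | 1.7% |
| 6 | 2.7% | 5.4% | 2.4% |
| 13 | 3.0% | 5.3% | 2.2% |

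The reference is 2.5%, the upper-tail half of the two-sided 0.05. Tested against a null of zero, every simulated trial gave P < 0.05.

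**The logit scale.** In the 74/116 case, logit(0.6378) = 0.566. The standard error is about 0.0446/(0.6378 × 0.3622) = 0.193. The lower limit is 0.566 − 1.96 × 0.193 = 0.188, which back-transforms to 54.7%, a fail. Across N = 116 to 129 with 2 to 13 missing, simulated one-sided error for logit pooling was about 2.2 to 2.7%. Power at 70% was about 88 to 94%, depending on N and the number missing.

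**The case against.** The strongest reply is that this path may seldom be taken and matters little if it is. The MI sentence is doubly conditional. Many gaps are closed first:
- Section 6.1 accepts thrill and bruit, or dialysis through the fistula, in place of Doppler, and scores earlier intervention as failure.
- Section 10.5.2 applies its deterministic rules, leaves out subjects with no post-procedure patency measurement, and excludes non-occluded deaths and transplants.
- Section 7.11 provides phone visits and record review.

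There are also backstops. The per-protocol analysis uses observed data only, and 10.6.7 adds worst-case and tipping-point analyses.

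Most of this stands, and it rules out three stronger readings that a reader might infer.
- *That the 10% dropout makes imputation the likely path.* That figure is the attrition from 129 to 116 evaluable. The documents give no count of values to be imputed.
- *That the error rate is 3.4% instead of 2.2%.* Those are the Wald rule (74 of 116) and the exact rule (75 of 116) on complete data. With nothing missing, MI is not triggered and the exact interval governs.
- *That the rule would be chosen after the data are seen.* The text leaves the choice open but does not say when it would be made.

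What the reply does not do is repair the step. Section 10.6.3 tests the primary hypothesis in the full analysis set, so the per-protocol and sensitivity analyses do not replace the missing decision rule. The tipping-point analysis itself needs a defined threshold for significance.

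**Conclusion.** The point holds in conditional form. When values are imputed, the instruction cannot be carried out as written, and its P-value is not the stated success criterion. The same applies to 10.6.4.

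The size is modest: about one success at the boundary and roughly 0.2 to 0.5 points of one-sided error above 2.5% under the two-sided reading, or about double the intended error if the P-value is read one-sided at 0.05. These figures rest on raw-scale pooling, which the plan does not prescribe, and on the missingness and imputation assumptions above.

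It would go too far to conclude that the confirmatory test is unworkable in general or the design unsound. The exact rule is complete when nothing is imputed, the sample size reproduces, and a workable pooled test is easy to specify.

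The absence of an imputation model from 10.5.2 carries less weight, because text may be missing from the public copy there. The main point rests on sentences in 10.6.3 that are intact. Severity: should fix.

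**What to change.** Replace the MI sentence in 10.6.3, and let 10.6.4 refer to it, with the following content:
- In each imputed data set compute logit(p) and its standard error 1/√(n·p·(1 − p)).
- Pool these in PROC MIANALYZE with the null set to logit(0.55).
- Back-transform the pooled two-sided 95% limits, and declare success only if the lower limit exceeds 55.0%.
- When nothing is imputed, the exact limit applies as now.
- Name the imputation model, its covariates and the number of imputations, all fixed before analysis.

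The cost is a paragraph of SAP text and a few lines of code, with no change to sample size or data collection. There is a small statistical price. The pooled test is approximate (simulated one-sided error about 2.2 to 2.7%), and a single imputed value switches the trial from the exact to the approximate rule. The logit is one workable scale among several. What matters is that the scale, the null value and the lower-limit rule are written down. A separate exact analysis of observed cases adds little, since the per-protocol analysis largely covers it, although that set also drops major protocol violators.
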